#### 4.5.1.3 Serious Adverse Events

An SAE, including a serious suspected adverse reaction or serious adverse reaction as determined by the PI or the Sponsor, is any event that results in any of the following outcomes:

- Death;
- Life-threatening adverse event (Life-threatening means that the study participant was, in the opinion of the PI or Sponsor, at immediate risk of death from the event as it occurred);
- Inpatient hospitalization or prolongation of existing hospitalization;
- Persistent or significant disability or incapacity or substantial disruption of the ability to conduct normal life function, or;
- Congenital abnormality/birth defect;
- Important medical events that may not result in one of the above outcomes but may jeopardize the health of the study participant or require medical or surgical intervention to prevent one of the outcome listed in the above definition of serious event.

#### All SAEs will be:

- Recorded on the appropriate SAE report form and sent to the Emmes Coordination Center within 24 hours of the site's knowledge of the event.
- Reported to the Emmes medical monitor who in turn will pass on the information to the Sponsor and SIIPL
- Reported to the site's Independent Safety Monitor
- Reviewed and followed until the event is resolved or determined to be irreversible, chronic, or stable by a study physician

SAEs will be collected on each participant for 180 days after vaccination.

#### 4.5.2 Immunogenicity Variables

Immunogenicity testing for Meningococcal serogroups A, C, Y, W and X specific antibodies using rSBA assay will be performed on sera collected at baseline (Day 1) and 28 days post vaccination (Day 29). The rSBA assay will be conducted at Vaccine Evaluation Unit at Public Health England (PHE) in Manchester UK. Additional immunogenicity assays may be performed by research laboratories to further evaluate post-vaccination immune responses. These exploratory analyses may be done on a subsample of participants' sera, if remaining specimen volume is adequate.

#### 5 SAMPLE SIZE CONSIDERATIONS

Since this study is a Phase 1 trial it is designed to provide preliminary safety and immunogenicity data that may support testing the study product in additional larger cohorts in adults and in age-descending studies.

With 20 vaccine recipients per vaccine group, this study's design allows a greater than 90% chance of observing an adverse event (AE) that has an 11% chance of occurrence. Conversely, if no AEs are observed in 20 vaccine recipients, the study will be able to rule out AEs occurring at a rate of approximately 14% based on the upper bounds of the one-sided 95% Confidence Interval (CI).

No formal statistical hypothesis testing is planned for this first time in human Phase 1 study whose objectives are aimed to descriptively evaluate the safety and immunogenicity profile of the study.

#### **6 GENERAL STATISTICAL CONSIDERATIONS**

#### **6.1** General Principles

All continuous variables will be summarized using the following descriptive statistics: n (non-missing sample size), mean, standard deviation, median, quartiles, and range (maximum and minimum). The number and percent of participants (based on the population sample size) of observed levels will be reported for all categorical measures. In general, all data will be listed, sorted by treatment and participant, and when appropriate by visit number within participant. All summary tables will be structured with a column for each treatment in the order of adjuvanted MCV-5, non-adjuvanted MCV-5, and Menactra® and will be annotated with the total population size relevant to specific tables/treatment, including any missing observations.

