#### STUDY PROCEDURES & VISIT SCHEDULE

After volunteers have signed the written informed consent, they will be screened for eligibility into the study. Screening will take place within 28 days prior to vaccination (Visit 1; Screening). A blood sample (up to 18 mL) will be taken at the screening visit for laboratory testing.

The following assessments will be conducted during the screening visit: medical history, physical examination, vital signs measurement and laboratory evaluation including hematology, serum chemistry and viral serology for Human immunodeficiency virus (HIV), Hepatitis B virus (HBV), and Hepatitis C virus (HCV). A test for pregnancy will be performed among females of child bearing potential. Inclusion/exclusion criteria will be assessed for eligibility.

At Visit 2 (Vaccination), eligible volunteers will be randomized in a 1:1:1 ratio to either one of the following groups:

Group	Vaccine
1 (n=20)	Adjuvanted Study vaccine (MCV-5)
2 (n=20)	Non-adjuvanted Study vaccine (MCV-5)
3 (n=20)	Reference vaccine (Menactra®, ACYW)

Baseline blood sample (20 mL) for immunogenicity testing will be collected before randomization on the day of vaccination and thereafter vaccine will be given as a single intramuscular injection of 0.5 mL in the deltoid. The day of vaccination will be considered as Day 1. After vaccination, participants will be observed for 60 minutes at the clinic to detect any immediate reactions or any other AE. All relevant information will be reported in the Case Report Form (CRF). A Memory Aid will be distributed and participants will be instructed to record post-immunization reactions, adverse events and concomitant medications. Participants will be informed to return to study centre for Visit 3 (Day 8).

At Visit 3 (Day 8), participants will undergo a targeted physical examination, vital sign measurement and a blood sample will be collected (up to 8 mL) to repeat the safety laboratory evaluations. Memory Aid records will be discussed with the participants, if needed, reconciled by the investigator/designee before recording in source document and transcribed into the CRF.

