#### 6.3 Analysis Populations

A tabular listing of all participants, visits, and observations excluded from the full analysis and per protocol populations will be provided in Listing 16.2.3.

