#### **6.3.2** Full Analysis Population

All participants in the enrolled population who were randomized and received a study vaccination will be included in the Full Analysis (FA) Population. All safety analyses will be performed using this population. Treatment groups for safety analysis will be assigned according to the actual treatment received at Day 1.

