#### **6.3.3** Per Protocol Population

All participants in the FA population who are assigned the study vaccination with no major protocol violations that are determined to potentially interfere with the immunogenicity assessment of the study vaccine and who have at least one immunogenicity assessment will be included in the Per Protocol (PP) population. This population will serve as the primary analysis population for the immunogenicity endpoints.

The criteria for exclusion of participants from the PP population will be established before breaking the blind and will be based on the blinded review of protocol violations.

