#### 8 IMMUNOGENICITY EVALUATION

The secondary and exploratory immunogenicity outcomes for the study are based on the rSBA titer for Meningococcal serogroup A, C, Y, W and X specific antibodies. For each participant, the rSBA titer will be measured at Day 1 prior to vaccination and at Day 29 (28 days post vaccination). All immunogenicity analyses will be conducted using the PP population and FA population. Individual participant data listings of immunogenicity will be presented in Listing 16.2.6.

Due to the hypothesis generating nature of multiple statistical comparisons for immunogenicity associated with multiple endpoints for this early phase FIH study, all estimations will be carried out using a two-sided 5% Type I error rate without an adjustment for multiple comparisons.

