#### 8.1 Secondary Endpoint - a 4-fold response in rSBA titer

The percentage of participants with a 4-fold response in rSBA titer against serogroups A, C, W, Y and X will be defined as follows:

- For participants with a pre-vaccination rSBA < 8, a post-vaccination titer >= 32.
- For participants with a pre-vaccination rSBA titer ≥ 8, a post-vaccination rSBA titer of at least 4 times the pre-vaccination titer.

The number and percentage of participants with a 4-fold response in rSBA titer will be summarized at Day 29, along with two-sided 95% exact confidence intervals (CIs) for each of the proportions. Two-sided exact 95% CIs for the three pair-wise proportion differences between the three treatment groups will be computed using the unconditional exact method proposed by Chan and Zhang (1999).(Note: In SAS, this is the RISKDIFF(METHOD=FMSCORE) option in PROC FREQ).

Table 14.2.1.1 will summarize the number and percentage of participants with a 4-fold response in rSBA titer for each of the five serogroups and 95% CIs for each treatment group and treatment group comparison. CIs will be visualized graphically in Forest plots as depicted in Figure 14.2.1.2.

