**TABLE 14.1.2: Analysis Populations by Treatment Group** 

	Adjuvanted MCV-5 (N=X)		Non-adjuvanted MCV-5 (N=X)		Menactra® (N=X)		All Participants (N=X)		
Analysis Populations	Reason Participants Excluded	n	%	n	%	n	%	%	n
	Any Reason	X	x.x	X	x.x	X	X.X	х	x.x
Full Analysis Population	Not Randomized	X	X.X	X	x.x	X	x.x	X	x.x
	Randomized but not vaccinated	X	X.X	Х	x.x	X	x.x	X	x.x
	Any Reason	X	X.X	X	X.X	X	x.x	X	X.X
Per Protocol Population	No Valid Immunogenicity Assessment	X	X.X	Х	X.X	X	x.x	X	X.X
	Major Protocol Violation	Х	X.X	Х	X.X	Х	x.x	Х	X.X

N=Number of participants enrolled in the study.

TABLE 14.1.3:
Participant Disposition by Treatment Group

Participant		ted MCV-5 =XX)		nted MCV-5 XX)		actra® =XX)	All Participants (N=XX)	
Disposition	n	%	n	n	n	%	n	%
Screened							xx	
Enrolled/Randomized	XX	100.0	xx	100.0	XX	100.0	xx	100.0
Received Vaccination	XX	XX.X	xx	XX.X	XX	XX.X	xx	xx.x
Completed Visit 3 (Day 8)	XX	XX.X	xx	XX.X	XX	XX.X	xx	xx.x
Completed Visit 4 (Day 29)	xx	XX.X	xx	XX.X	XX	XX.X	xx	XX.X
Completed Visit 5 (Day 85)	XX	XX.X	xx	XX.X	XX	XX.X	xx	XX.X
Completed Follow-up at 6 Months Post-Vacc a	xx	XX.X	xx	XX.X	XX	XX.X	xx	XX.X
Per Protocol population b	XX	XX.X	xx	XX.X	XX	XX.X	xx	XX.X
Early Termination / Reason								
Any reason	xx	XX.X	xx	XX.X	XX	XX.X	xx	xx.x
SAE (other than death)								
AE (other than SAE)								
Lost to follow-up								
Non-compliance / protocol deviation								
Voluntary withdrawal								
Withdrawn by investigator								
Termination of site or study by sponsor								
Death								
Enrolled but not vaccinated								
Other								

N=Number of participants enrolled in the study.

<sup>a Refer to Listing 16.2.1 for reasons participants discontinued or terminated early.

<sup>b Refer to Listing 16.2.3 for reasons participants are excluded from the immunogenicity analysis.

TABLE 14.1.4.1: Summary of Demographic and Baseline Characteristics by Treatment Group - Full Analysis Population

Statistic	Adjuvanted MCV-5 (N=X)	Non-adjuvanted MCV-5 (N=X)	Menactra® (N=X)	All Participants (N=X)
Sex, n (%)				
Male	x (x.x)	x (x.x)	x (x.x)	x (x.x)
Female	x (x.x)	x (x.x)	x (x.x)	x (x.x)
Ethnicity, n (%)				
Not Hispanic or Latino	x (x.x)	x (x.x)	x (x.x)	x (x.x)
Hispanic or Latino	x (x.x)	x (x.x)	x (x.x)	x (x.x)
Not Reported	x (x.x)	x (x.x)	x (x.x)	x (x.x)
Unknown	x (x.x)	x (x.x)	x (x.x)	x (x.x)
Race, n (%)				
American Indian or Alaskan Native	x (x.x)	x (x.x)	x (x.x)	x (x.x)

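### SAP 6.1 puts seroresponse percentages on the population size and SAP 8.1–8.2 name no other denominator, so a missing Day 29 titer would count against response in the Full Analysis tables; solicited-event denominators also conflict

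*SAP*

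**What the plan says.** **Seroresponse.** SAP 6.1 treats the two kinds of variable differently. Continuous variables are summarized on the non-missing sample size. For categorical ones: "The number and percent of participants (based on the population sample size) of observed levels will be reported for all categorical measures". It adds that summary tables show the total population size, missing observations included.

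SAP 8.1 says "The number and percentage of participants with a 4-fold response in rSBA titer will be summarized at Day 29", with exact confidence intervals and pairwise differences. SAP 8.2 does the same for titers of at least 8 and at least 128 at Day 1 and Day 29. Neither names a denominator or says what to do with an absent titer. The shells of Tables 14.2.1.1 and 14.2.2.1 print N without defining it.

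On populations, SAP 8 states: "All immunogenicity analyses will be conducted using the PP population and FA population". Full Analysis (FA) membership needs no titer (SAP 6.3.2): "All participants in the enrolled population who were randomized and received a study vaccination will be included in the Full Analysis (FA) Population". Per Protocol (PP), the primary immunogenicity population, takes FA participants without a relevant major violation "and who have at least one immunogenicity assessment will be included in the Per Protocol (PP) population" (SAP 6.3.3). SAP 6.5 treats missing data as missing completely at random, with imputation for safety endpoints only.

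**Solicited events.** SAP 9.4 divides adverse-event incidence by the total population. SAP 9.4.2 divides by participants with non-missing data for the event and ties that rule to Table 14.3.1.3. That table's footnote nevertheless defines N as the FA population, and its shell has no Not Reported row, although SAP 6.5 says unreported solicited symptoms will be shown as such. Table 14.3.1.2, with the confidence intervals and Fisher p-values, gets no rule of its own in 9.4.2 and so falls under 9.4.

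**The concern.** Dividing by everyone vaccinated while counting only observed responders has the same effect as imputing non-response for each missing titer. SAP 6.5 says immunogenicity data will not be imputed. If titers really are missing completely at random, as 6.5 assumes, the population denominator biases the response rate downward. It also creates a spurious difference between arms when their missing counts differ.

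Two of the three secondary endpoints are affected. They also feed the unblinded interim summary on the first 30 participants (SAP 6.6), which is meant to help plan the next trials. Two programmers could each defend a different percentage from the same SAP.

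For solicited events, Tables 14.3.1.2 and 14.3.1.3 could print different percentages for the same symptom in the same arm.

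**Working it through.** **Plan's own figures.** With n = 20 per arm and an 11% event rate, the chance of at least one event is 1 − 0.89^20 = 0.903 (stated as above 90%). With 0/20 events, the one-sided 95% upper bound is 1 − 0.05^(1/20) = 0.139 (stated as about 14%). Both reproduce. Neither depends on the denominator question.

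**Seroresponse inputs.** n = 20 per arm (SAP 4.1). m = number of Day 29 titers missing in an arm. The documents give no rate, so m = 1 to 3 is an assumption. x = responders among the 20 − m observed. Available-data rate = x/(20 − m); population rate = x/20. Intervals are two-sided 95% Clopper-Pearson.

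| m | Responders | Available data | Population size |
|---|---|---|---|
| 1 | 19 | 19/19 = 100% (82.4–100) | 19/20 = 95% (75.1–99.9) |
| 2 | 18 | 18/18 = 100% (81.5–100) | 18/20 = 90% (68.3–98.8) |
| 3 | 17 | 17/17 = 100% (80.5–100) | 17/20 = 85% (62.1–96.8) |
| 2 | 15 | 15/18 = 83.3% (58.6–96.4) | 15/20 = 75.0% (50.9–91.3) |

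The first three rows assume that every observed titer responds, which gives the widest gap. The last row is near the 83% four-fold response that Protocol 1.3.4 reports for the monovalent serogroup A vaccine; the gap is 8.3 points instead of 10. With m = 0 the two columns agree. With two titers missing in one arm, none in another and all observed titers responding, the between-arm difference is 10 points on the population size and 0 on available data.

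Interim: if the first 30 form five complete blocks of six (Protocol 2.4.7), there are 10 per arm. One missing titer then gives 9/9 = 100% (66.4–100) or 9/10 = 90% (55.5–99.7).

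**Does PP escape?** The Protocol synopsis says: "Baseline blood sample (20 mL) for immunogenicity testing will be collected before randomization on the day of vaccination". A baseline sample alone could therefore meet the one-assessment condition. The PP exclusion reason in Table 14.1.2, "No Valid Immunogenicity Assessment", names no visit. Against that, blinded review could exclude such a person, and SAP 6.3 allows for exclusion by visit: "A tabular listing of all participants, visits, and observations excluded from the full analysis and per protocol populations will be provided in Listing 16.2.3". The effect in PP is possible but not established.

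**Solicited events.** Assume 2 of 20 without data and the Menactra rates in Protocol 13.2.
- Pain: 0.539 × 18 = 9.7, about 10 reporters, so 10/18 = 55.6% (9.4.2) against 10/20 = 50.0% (9.4).
- Chills: 0.097 × 18 = 1.7, about 2 reporters, so 2/18 = 11.1% against 2/20 = 10.0%.

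The pain gap arises only if the 60-minute check alone does not count as non-missing data. That check records pain but does not list chills or vomiting (Protocol 5.2.4).

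Fisher tests: with m missing in the MCV-5 arm and none in Menactra, I compared denominators 20 − m and 20 over every possible pair of counts. The two-sided p crosses 0.05 in 16 of 420 pairs (3.8%) for m = 1, 30 of 399 (7.5%) for m = 2 and 42 of 378 (11.1%) for m = 3. These are unweighted counts, not probabilities. Weighted by binomial probabilities with a common true rate of 9.7%, 23.6% or 53.9% and m = 1 or 2, the chance of a flip is about 0.9% to 1.8% per comparison.

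**The case against.** The strongest reply is that 6.1 is a general principle, while 6.5 is the section written for missing data. A statistician could let 6.5 govern and analyze available titers. That is reasonable, but 6.5 sets no denominator. 6.1 does set one, for all categorical measures, and contrasts it with non-missing n for continuous ones. The text leaves the two in conflict.

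A reader might infer that the SAP deliberately counts missing titers as non-response. No section says so; it is only the consequence of applying 6.1 as written. A reader might also infer that the primary immunogenicity analysis is affected. PP is primary, and there the effect needs a baseline-only participant who survives both blinded review and visit-level exclusion. Nor does the different n behind the GMTs contradict the percentages: it follows from 6.1's own convention, and a GMT cannot use an absent titer.

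Keeping every vaccinated participant in the FA denominator is a recognized conservative choice. That stands, provided it is declared and labelled.

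On solicited events, 9.4.2 can be read as a specific exception to 9.4, and Table 14.3.1.4 does show a Not Reported row by day. This explains part of the difference. It does not explain why the Table 14.3.1.3 footnote departs from 9.4.2, or why Table 14.3.1.2 uses a different base for the same symptoms.

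The impact is limited. There is no formal hypothesis testing, the Fisher tests are an unadjusted screen, early-termination visits try to obtain the immunogenicity specimen (Protocol 5.4), and individual titers are listed.

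**Conclusion.** The point holds for the FA seroresponse tables as written, and only conditionally for PP. Each missing Day 29 titer in an arm of 20 lowers the rate by about 4 to 5 points when observed response is between roughly 83% and 100%. The 95%, 90% and 85% figures rest on an assumed 1 to 3 missing titers and full response among those observed.

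The solicited-event conflict is real on the page: three statements, two denominators. Its numerical effect is probably small, because most solicited events are also recorded at 60 minutes, and a change in a Fisher result is uncommon.

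Importance is minor to moderate. With complete data nothing changes, and no decision rule uses these percentages.

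**What to change.** **Seroresponse.** In SAP 8.1–8.2 and the shells, for both FA and PP:
- compute seroconversion on participants with both a Day 1 and a Day 29 titer for that serogroup;
- compute the proportions at or above 8 and 128 on participants with a titer at that visit;
- print the evaluable n and the number missing in each row.

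The PP definition need not change. Missing counted as non-response may be kept as a labelled FA sensitivity analysis.

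**Solicited events.** Choose one denominator for each event and use it in Tables 14.3.1.2 and 14.3.1.3, their footnotes and the Fisher tests. Say whether the 60-minute check alone makes an event non-missing, and add a Not Reported count.

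**General sections.** Add to 6.1 and 9.4 that their denominators apply unless a section names another.

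**Cost.** SAP wording and shell footnotes only; no new data. The downside is that denominators will vary by row and serogroup, and the available-data rates rely on the missing-completely-at-random assumption already made in 6.5.

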#### **6.2** Timing of Analyses

Analysis of all available safety data up to Day 29 post-vaccination for all 60 participants and all immunogenicity data for the first 30 participants will be performed as soon as the immunogenicity data become available (see Section 6.6). The final analysis will be performed after the completion of the study. Extensive safety monitoring will be ongoing throughout the study.

#### 6.3 Analysis Populations

A tabular listing of all participants, visits, and observations excluded from the full analysis and per protocol populations will be provided in Listing 16.2.3.

#### **6.3.1** Enrolled Population

All screened participants who provide informed consent (IC), regardless of the participant's randomization and treatment status in the trial, will be included in the enrolled population.

#### **6.3.2** Full Analysis Population

All participants in the enrolled population who were randomized and received a study vaccination will be included in the Full Analysis (FA) Population. All safety analyses will be performed using this population. Treatment groups for safety analysis will be assigned according to the actual treatment received at Day 1.

#### **6.3.3** Per Protocol Population

All participants in the FA population who are assigned the study vaccination with no major protocol violations that are determined to potentially interfere with the immunogenicity assessment of the study vaccine and who have at least one immunogenicity assessment will be included in the Per Protocol (PP) population. This population will serve as the primary analysis population for the immunogenicity endpoints.

The criteria for exclusion of participants from the PP population will be established before breaking the blind and will be based on the blinded review of protocol violations.

#### 6.4 Covariates and Subgroups

There is no a priori plan to summarize the immunogenicity or safety endpoints for covariates or subgroups. The protocol does not define any formal subgroup analyses and the study is not adequately powered to perform subgroup analyses.

#### 6.5 Missing Data

In general, all missing data will be treated as missing completely at random and no imputation will be performed except for the safety endpoints as described below. Non-analyzable data (e.g., due to major protocol violations) will be documented in the deviations. For immunogenicity data where the antibody titer is below 1:8 (< 8), an arbitrary value of half the assay's cut-off value, 4, will be used in the analyses for those values.

If some safety data are available for a participant in the FA population, but respective secondary endpoint related data are missing, then the participant will be included in the safety analysis and data will be treated as follows for immediate AEs, unsolicited AEs and serious adverse events (SAEs).

- If Severity is missing for any AE, then it will be considered as an AE of maximum severity (Grade 3) "Severe", unless it is captured as SAE.
- If "Relationship" is missing, then it will be considered as "Related" to the vaccine administered.
- If, for Start date, the day of event/condition is missing due to any adverse event, then it will be imputed as the date of last dose of study vaccine.
- If the Stop date of an adverse event is missing, then it will be treated as ongoing.

For solicited adverse events, the following assumptions will be made:

- If dates are missing, but symptoms are reported, then the day post vaccination will be used to calculate the date of the symptom.
- If a symptom is not reported at any time through Day 7, then no imputation for missing data will be performed. The data will be summarized as not reported on the tables.

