#### 7.5.2. Statistical Method

When the use of descriptive statistics to assess group characteristics or differences is required, the following methods will be used: for categorical variables, the number and percent of participants in each category; for continuous variables, the mean, median, standard deviation, quartiles and range (minimum, maximum).

In general all missing data will be treated as missing completely at random and no imputation will be performed except for the safety endpoints as described below. Non-analyzable data (e.g., due to major protocol violations) will be documented in the deviations.

If some safety data are available for a subject in the safety population but respective secondary endpoint related data are missing then the subject will be included in the safety analysis and data will be treated as follows for immediate AEs, solicited AEs, unsolicited AEs and SAEs.

- 1. If Severity is missing for any AE then it will be considered as an AE of maximum severity (Grade 3) "Severe" unless it's captured as SAE.
- 2. If "Relationship" is missing then it will be considered as "Related" to the vaccine administered.
- 3. If, for Start date, the day of event/condition is missing due to any adverse event then it will be imputed as the date of last dose of study vaccine.
- 4. If, for Start date, the day and month of an adverse event is missing, then it will be imputed as the date of first dose of study vaccine.
- 5. If the Stop date of an adverse event is missing then it will be treated as ongoing.

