#### 3.1.2 Secondary Objective

The secondary objective is to assess the immune response of adjuvanted and non-adjuvanted formulations of MCV-5 vaccine.

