#### 3.2.2 Secondary Endpoints

- The percentage of participants who show a seroconversion for Meningococcal Polysaccharide (PS) A, C, Y, W and X specific antibodies, i.e., a ≥4-fold increase in post-immunization rabbit complement serum bactericidal activity (rSBA) titer with respect to pre-immunization rSBA titer, at 28 days after a single vaccine dose.
- The percentage of participants who show a post-immunization seroprotection titer for Meningococcal PS A, C, Y, W, and X specific antibodies, defined as rSBA titer of ≥1:8 and ≥1:128 at 28 days after a single vaccine dose.
- Geometric Mean Titers (GMTs) of Meningococcal PS A, C, Y, W and X serogroup-specific antibodies at 28 days after a single vaccine dose, as measured by rSBA assay.

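### The lead-in of SAP 6.5 and protocol 7.5.2 ties the worst-case rules for incomplete adverse event records to missing rSBA data, which leaves the scope of those rules ambiguous

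*SAP*

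**What the plan says.** SAP 6.5 treats missing data as missing completely at random and states that "no imputation will be performed except for the safety endpoints as described below". The description that follows, for immediate AEs, unsolicited AEs and SAEs, opens with a two-part condition: some safety data are available for a Full Analysis participant, "but respective secondary endpoint related data are missing, then the participant will be included in the safety analysis". The same sentence then says how the data will be treated, and the rules hang on it:

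- Missing severity: the rule begins "If Severity is missing for any AE, then it will be considered as an AE of maximum severity (Grade 3" and makes an exception for events captured as SAEs.
- Missing relationship: counted as related.
- Missing start day: set to the date of the last vaccine dose.
- Missing stop date: treated as ongoing.

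Protocol 7.5.2 carries the same condition ("but respective secondary endpoint related data are missing then the subject will be included in the safety analysis"), so neither document corrects the other. Its list of event types also includes solicited AEs, which the SAP list omits.

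The term secondary has a fixed meaning here. Under SAP 3.1.2, "The secondary objective is to assess the immune response of adjuvanted and non-adjuvanted formulations of MCV-5 vaccine". The three endpoints in SAP 3.2.2 are 4-fold response, titers at or above two cut-offs, and "Geometric Mean Titers (GMTs) of Meningococcal PS A, C, Y, W and X serogroup-specific antibodies at 28 days after a single vaccine dose". All are rSBA measures.

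**The concern.** A missing titer says nothing about whether an adverse event has a grade or an attribution. Suppose two participants have identical adverse event records with the relationship left blank, and one has a Day 29 titer while the other does not. Read literally, the event counts as related in the participant without the titer. In the participant with the titer, the no-imputation default applies and no rule says how to count it.

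The rows at stake in the primary summary (SAP 9.4.1, Table 14.3.1.1) are Grade 2+ unsolicited, related unsolicited, and Grade 2+ related unsolicited events. Relatedness also bears on the primary hypothesis, because protocol 7.1 requires that no participant develop a vaccine-related SAE.

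The interim analysis adds a complication. SAP 6.2 and 6.6 combine Day 29 safety data for all 60 participants with titers for only the first 30. The text does not say whether a result still awaited counts as missing. If it does, the literal condition would treat the first 30 and the later 30 differently, in an unblinded output used to plan further trials.

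**Working it through.** **1. The plan's own figures reproduce.** SAP section 5 gives n = 20 per group.

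- Chance of seeing at least one event with 11% incidence: 1 − 0.89^20 = 0.903 (stated: above 90%).
- One-sided exact 95% upper bound for 0/20: 1 − 0.05^(1/20) = 13.9% (stated: approximately 14%).

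**2. The text, set side by side.**

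- The default is no imputation, with an exception for safety endpoints as then described (SAP 6.5).
- The only description of the severity and relationship rules sits under the secondary-endpoint condition (SAP 6.5, protocol 7.5.2).
- Secondary endpoints are rSBA endpoints (SAP 3.2.2, protocol 7.3.2).
- The half of the sentence that includes such participants in the safety analysis adds nothing. SAP 6.3.2 already covers everyone randomized and vaccinated: "All safety analyses will be performed using this population".
- SAP 9.4 puts every reported event into the summaries, so an incomplete record stays in the any-unsolicited-AE row under either reading.
- No section states how an ungraded or unattributed event is tabulated when titers are present. The shell of Table 14.3.1.7 lists mild, moderate, severe, life-threatening and death, with no category for a missing grade.

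**3. Effect of one record on one row.** Take one ungraded non-serious unsolicited event in a participant with titers, in an arm of 20 where nobody else has a Grade 2+ unsolicited event. Intervals are exact (Clopper-Pearson).

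| Reading | Row | Two-sided 95% CI | One-sided 95% upper bound |
|---|---|---|---|
| Literal condition, not imputed | 0/20 = 0% | 0% to 16.8% | 13.9% |
| Rules apply to all | 1/20 = 5% | 0.1% to 24.9% | 21.6% |

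The same change applies to the related row for one unattributed event. If the participant already has another event qualifying for that row, nothing changes.

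**4. Effect on the chance of detection.** The documents give neither the share d of participants without rSBA data nor the share m of relevant events left ungraded. Both are assumed here. With unimputed events lost to the row, the chance of seeing at least one Grade 2+ event of 11% true incidence in 20 is 1 − [1 − 0.11 × (1 − m(1 − d))]^20.

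| m | d = 0 | d = 10% |
|---|---|---|
| 0 | 90.3% | 90.3% |
| 1% | 90.0% | 90.1% |
| 5% | 89.0% | 89.1% |
| 10% | 87.6% | 87.9% |
| 20% | 84.2% | 84.9% |

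**5. Who falls outside the condition.** With d = 0%, 5% or 10%, that is 60, 57 or 54 of the 60 participants. This counts participants for whom the literal condition is false. It does not count affected adverse events.

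**The case against.** The strongest reply is that this is loose drafting with an obvious meaning. The opening sentence exempts safety endpoints generally, the severity rule is worded for any AE, and the clause says if, not only if, without naming rSBA. On that view it is a misplaced reminder that a participant without titers still counts for safety, and no programmer would make an AE grade depend on a titer. This is probably the right account of the intent, and the lack of a missing-grade category in Table 14.3.1.7 fits it. It does not settle the wording: the rules follow grammatically from the condition, and no other text supplies them.

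The reply also points out that blank fields should be rare, and this stands:

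- The site grades severity and makes a related/unrelated call (protocol 8.4, 8.5).
- The investigator assigns or reviews both for SAEs (8.7.3), and the medical monitor comments on the relationship (8.8.1).
- The data system checks for incomplete entries (10.1), and queries are resolved before close-out (section 11).
- Final lock requires a case-by-case review of AE severity (10.3).

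A reader might infer that the rules definitely exclude nearly every participant, and that incomplete events therefore drop out of the safety results. The documents do not support this. Exclusivity is an inference from the condition, the any-unsolicited-AE row is unaffected, and a high share of participants with titers says nothing about how many events have a blank field.

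**Conclusion.** The defect is real but narrow. As worded, both documents attach the worst-case rules to a condition that is irrelevant to them. Followed literally with the no-imputation default, this leaves incomplete AE records in participants with titers without a rule for the Grade 2+ and related unsolicited rows. The size is conditional: one affected record in an arm with no other qualifying participant moves the row from 1/20 to 0/20, and the one-sided upper bound from 21.6% to 13.9%. The latter is the value the plan associates with no events observed. The number of such records is unknown and may be zero. On the assumed shares above, the loss in detection chance is 0.2 to 1.3 percentage points at m of 1% to 5%. A lasting bias in the reported safety profile cannot be claimed from the documents. What can be claimed is an ambiguous rule on primary safety rows, best settled before unblinding.

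**What to change.** Delete the secondary-endpoint condition from SAP 6.5 and put in its place a sentence to this effect: for every participant in the Full Analysis population, a missing severity, relationship, start date or stop date of an immediate AE, unsolicited AE or SAE is handled by the rules listed below, regardless of immunogenicity data.

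In the same edit, reconcile whether solicited AEs are covered. Protocol 7.5.2 includes them in the worst-case rules. SAP 6.5 leaves them out and gives them separate handling for dates and unreported symptoms, with no rule for a reported symptom that lacks a grade.

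Amend protocol 7.5.2 to match, or record the departure from it in SAP section 12, which at present has a heading and no text.

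The cost is a few sentences and no new data. The downside is that safety rates may become slightly less favourable.
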